An optional part of the study protocol, a subcohort of at least 200 patients (funds allowing) will be offered a routine 30-day post-RP screening lower extremity Duplex ultrasound to assess for DVT at Johns Hopkins for patients willing to travel to Johns Hopkins to obtain the ultrasound in this time frame. Patients are not required to obtain this screening ultrasound, but initial randomization will be stratified by whether patients opt to undergo ultrasound (and robotic vs. open surgery) to ensure study arms are balanced. In other words, patients willing to undergo ultrasound will be identified before randomization. All patients, regardless of whether they undergo ultrasound, will be assessed for all primary outcomes as described. For the subset of patients who obtain the ultrasound, it will be used to assess the secondary outcome of any VTE (asymptomatic or symptomatic). The outcome of any VTE will be tabulated based on the results of the screening ultrasound and any report of a symptomatic VTE episode (assessed by call at 30 days as described above). Stratified randomization is outlined in Figure 1. Written informed consent includes a plan to inform the patient and their primary physician of the results of the ultrasound and any incidental findings. Costs for the screening ultrasound obtained as part of the study will be covered by the study. Symptoms prompting a recommendation for evaluation to rule out DVT or PE (appropriate diagnostics/imaging to be determined by evaluating physician) will include:

1. Persistent unilateral or bilateral lower extremity edema
2. Persistent calf pain or cramping
3. Persistent or new chest pain
4. Persistent or new shortness of breath that started suddenly or worsens with exertion
5. Productive cough with bloody sputum
6. Fever and/or tachycardia without any known source of infection
7. Any other clinical concern for DVT or PE

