Urologists will initially be blinded to patient randomization and the administration of the preoperative subcutaneous heparin dose to prevent bias on recorded estimated blood loss during the surgery. Postoperatively, administration of subcutaneous heparin will be unblinded during the patient's inpatient stay. Control patients will receive IPCs only and no placebo doses will be administered during their hospital stay. Data analysis will be blinded as to treatment group. Performance and interpretation of lower extremity Duplex screening ultrasound will be blinded to patient randomization. Surveillance bias will be assessed by differential performance of postoperative imaging as described above.

- d. Justification of why participants will not receive routine care or will have current therapy stopped.

All patients will receive routine care. Both arms include patients receiving accepted standards of care.

- e. Justification for inclusion of a placebo or non-treatment group.

The control group in this trial is the group receiving current routine practice at Johns Hopkins with IPCs. The experimental group is the group receiving pharmacologic VTE prophylaxis as practiced at other centers and recommended by most VTE guidelines for major surgery.

- f. Definition of treatment failure or participant removal criteria.

Participants will be removed from the trial if surgery is canceled or not completed for any reason. All patients assigned to the experimental and control arms completing surgery will be included in the study regardless of compliance with pharmacologic prophylaxis doses in an intention-to-treat (ITT) analysis. Patients experiencing an adverse event will be provided appropriate care. Additional per-protocol analyses will be conducted to compare outcomes by compliance with assigned regimen. Patients diagnosed with VTE events will be recommended to obtain routine care locally or at Johns Hopkins per patient preference.

- g. Description of what happens to participants receiving therapy when study ends or if a participant's participation in the study ends prematurely.

Perioperative pharmacologic prophylaxis is only given during the patient's inpatient stay. As mentioned above, all patients will be included in an ITT analysis as possible if they undergo surgery. No planned outcomes will be tracked after the 30-day post-surgical outcomes unless the patient initiates contact.

5. Inclusion/Exclusion Criteria

Inclusion:

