Randomization by blocks will be used, with stratification for type of surgery (robotic/laparoscopic vs. open) and subcohort membership (agrees to 30 day ultrasound/does not agree to 30 day ultrasound). Currently at Johns Hopkins approximately 40% of RPs are performed open, with the remainder robotic or laparoscopic, and the subcohort is planned to include 200 patients. Note that patients are randomized within each of the 4 subgroups formed by cross classification of these 2 strata, not randomized to the strata. Therefore, anticipated sizes of the 4 strata are

1. open RP/subcohort member, n=80
2. open RP/not subcohort member, n=186
3. robotic RP/subcohort member, n=120
4. robotic RP/not subcohort member, n=280

Because the above numbers are subject to variability in the choice of surgical approach, randomization lists will increase the number in each of the surgical categories by 20%, i.e. 320 and 480 random assignments will be generated for open and robotic surgeries, respectively. An undisclosed block size will be used to prevent any ability to predict next treatment assignment. The randomization lists will be generated by [name] using SAS PROC PLAN. Although this uses a pseudorandom number generator it has the advantage of reproducibility when the same seed is used. [name] will maintain the randomization list, password protected, on a remote drive maintained by the Department of Urology, and will provide the random assignment to the study coordinator as each patient is enrolled. Because surgery dates are scheduled weeks in advance, there is no concern about inability to access the randomization list. A biostatistician who works for [name] and is not otherwise connected to this trial will also have access to the random assignments and can provide them to the study coordinator in the unlikely event that [name] is unavailable. Only [name] and the biostatistician ([name]) have access to the remote drive.

b. Primary outcome variable.

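### Keeping one block size undisclosed does not prevent prediction of the next assignment; the plan should specify randomly varying blocks and keep recruiters away from the running sequence

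*Combined protocol and SAP*

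**What the plan says.** Section 7a plans blocked randomisation stratified by surgical approach and by agreement to the 30-day ultrasound: "patients are randomized within each of the 4 subgroups formed by cross classification of these 2 strata, not randomized to the strata". On block size it says only: "An undisclosed block size will be used to prevent any ability to predict next treatment assignment". It gives no size and does not say whether the size varies.

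The list is password protected and open to two people, its holder and a biostatistician otherwise outside the trial. The holder "will provide the random assignment to the study coordinator as each patient is enrolled".

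Four other sections bear on the point:

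- **Section 4a.** Consent may be taken at the urology visit, at the preoperative evaluation visit, or in the preoperative area on the day of surgery. Randomisation follows consent and scheduling. On the ultrasound subcohort, "patients willing to undergo ultrasound will be identified before randomization".
- **Section 4c.** Urologists are blinded at first. Then: "Postoperatively, administration of subcutaneous heparin will be unblinded during the patient's inpatient stay". Control patients receive no placebo.
- **Section 5, exclusion 2.** This rests on the judgement of the urologist or the preoperative evaluation centre.
- **Section 7d.** Accrual is planned on the assumption that 50% of patients enrol.

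**The concern.** The plan credits its method with a property that permuted blocks do not have. Each block must end in balance, so anyone who knows the assignments so far in a stratum has information about the next one. Hiding the block size weakens that information but does not remove it, and a size that never changes can be learned from the sequence.

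Concealment of the next assignment guards against selective enrolment. If someone who influences consent or eligibility can anticipate the next arm, men seen as higher or lower risk for clots or bleeding could be enrolled, deferred or excluded accordingly. Under the design assumptions the primary comparison rests on few events: 333 × 0.05 + 333 × 0.015 = 16.65 + 5.00, or about 22. Baseline adjustment can correct only for risk factors that were measured.

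**Working it through.** **The plan's own figures.** The documents give no figure for predictability. The figures that set the scale do reproduce:

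- The strata are "open RP/subcohort member, n=80", "open RP/not subcohort member, n=186", "robotic RP/subcohort member, n=120" and a fourth of 280 (robotic, not in the subcohort). 80 + 186 + 120 + 280 = 666.
- List lengths: 266 × 1.2 = 319.2, given as 320; 400 × 1.2 = 480.
- Power for 333 per arm, 5% against 1.5%, one-sided 0.05: 0.818 with a single look, and 0.825 by simulation with O'Brien-Fleming-type boundaries and the stated interim futility limits. The plan states 82%.

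**Assumption.** Block size is not given. Results are shown for 4, 6 and 8. The observer is assumed to regard even sizes from 2 to 12 as possible.

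**Step 1. Guessing without knowing the size.** The observer guesses the arm that is behind in the stratum. For block size 2m the expected share correct is [m + (4^m / C(2m, m) − 1) / 2] / (2m).

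- m = 2: [2 + (16/6 − 1)/2] / 4 = 70.8%
- m = 3: [3 + (64/20 − 1)/2] / 6 = 68.3%
- m = 4: [4 + (256/70 − 1)/2] / 8 = 66.6%

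Chance alone gives 50%.

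**Step 2. Size known.** The share of assignments that are forced is 1/(m + 1): 1/3, 1/4 and 1/5 for sizes 4, 6 and 8. Of 666 that is 222, about 167 and about 133. This is an upper limit, because the plan does keep the size undisclosed.

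**Step 3. Size not known.** The four strata were simulated at their stated sizes. The observer updates a probability for each candidate size after every assignment. An assignment counts as near-certain when its predicted probability is at least 99%. Learning is either separate in each stratum or pooled across strata.

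| Scheme | Near-certain, separate | Near-certain, pooled | Best guess correct |
|---|---|---|---|
| Fixed 4 | 25.5% | 31% | 71% |
| Fixed 6 | 18.5% | 23% | 68% |
| Fixed 8 | 16.7% | 19% | 67% |
| Mixed 4/6/8 | about 2% | about 3% | 68% |

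The mixed-block observer knows the set of sizes but not their order.

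**Step 4. Speed of learning.** Within one stratum, candidate sizes that are not multiples of the true size are ruled out after a median of 50, 32 and 36 assignments for true sizes 4, 6 and 8. That is 50/4 = 12.5, 32/6 = 5.3 and 36/8 = 4.5 blocks. In the stratum of 80, 50 assignments is 50/80 = 62.5% of the stratum.

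**Step 5. Possible effect on the result.** This is an illustration on assumptions that are not in the documents: no true effect, mean risk 5%, block size 4, and steering that shifts a man's risk by ±d according to the guessed arm, in the direction that favours heparin. With guess accuracy a and fraction steered f, the spurious difference is 2d(2a − 1)f.

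- f = 10%, d = 1 to 2 points: 2 × 0.01 × 0.4167 × 0.1 = 0.08 points, up to 0.17 points. One-sided error rises from 0.05 to between 0.055 and 0.061.
- f = 100%, same d: 0.83 to 1.67 points. One-sided error is 0.125 to 0.255.

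**The case against.** The strongest reply is that the plan already protects concealment in the ways that matter most. The list is locked and held by two people. Each assignment is released only at enrolment, after consent and scheduling. Surgical approach and ultrasound choice must both be known before a stratum list can be used. Urologists are blinded until after surgery. Because operations are scheduled weeks ahead, what is seen on the ward lags behind the assignments being made, and an observer who does not track strata guesses only 58% to 61% correctly for fixed sizes 4 to 8. Withholding block details from a protocol is itself sound practice. Section 7d also allows logistic regression for imbalanced confounders.

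Much of this stands, and it rules out three stronger readings that a reader might infer.

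- **That the block size is certainly fixed.** The text is singular but says neither that the size is constant nor that it varies. What can be said is that variation is not specified.
- **That enrolment or stratum choice would be steered.** The documents give the coordinator no role in consent, eligibility, surgical approach or ultrasound choice, and section 8c allows for more than one coordinator. Exclusion 2 and the several consent points are opportunities only.
- **That mixed blocks make assignments unpredictable.** Best-guess accuracy is 68% with mixed sizes, against 67% to 71% with fixed sizes, and is slightly worse than with fixed 8.

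The safeguards do not answer the narrower point. They hide the actual next assignment but do not prevent an inference from past ones before consent is sought. Nothing says who recruits, or that recruiters are kept from the sequence. Regression handles measured risk factors only.

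**Conclusion.** The purpose claimed in section 7a is not met by the method described. Read as one fixed size of 4 to 8, the scheme would let an observer who tracks the strata predict roughly 17% to 31% of assignments with near-certainty, or about 111 to 206 of 666, even without being told the size. Randomly mixed blocks of 4, 6 and 8 bring this down to about 2% to 3%. These figures assume a diligent observer who sees every assignment with its stratum, and candidate sizes from 2 to 12.

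The consequence for the result is a possibility, not a finding. On the illustrative assumptions, steering one patient in ten adds at most about 0.01 to the one-sided error rate; a large distortion needs steering to be widespread. The change is worth making because it is almost free and the present wording promises more than the method delivers.

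**What to change.** In section 7a:

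1. Specify permuted blocks of randomly varying size, generated within each of the four strata, with sizes and their order undisclosed to site staff.
2. Replace the claim that prediction is prevented with a statement that predictability is reduced.
3. State that those who obtain consent and judge eligibility do not see the running sequence of assignments. Varying the blocks leaves best-guess accuracy almost unchanged, so this item matters as much as the first.

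If the list program already varies the sizes, only the text needs to change. Otherwise the cost is a few lines of code before the lists are used, and a slightly larger possible imbalance within a stratum. Sample size and power are unchanged, and no patients are added.

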Specific aims: Does the use of perioperative pharmacologic agents (subcutaneous heparin; 5,000 units given before surgery and every 8 hours after surgery until discharge), compared to IPCs alone, for RP for prostate cancer:

1. Prevent the occurrence of symptomatic VTE following surgery? (primary efficacy outcome)
2. Increase the incidence of clinically significant lymphocele? (primary safety outcome)
3. Increase the incidence of clinically significant hematoma? (primary safety outcome)
4. Increase the incidence of major bleeding following surgery? (primary safety outcome)
5. Prevent the occurrence of any VTE (asymptomatic or symptomatic) following surgery? (secondary outcome)
6. Increase estimated blood loss during surgery? (secondary outcome)
7. Increase surgical drain output after surgery? (secondary outcome)

8. Lead to potential surveillance bias measured by increased or decreased use of diagnostic imaging for VTE relative to symptoms (e.g. lower extremity Duplex ultrasound, spiral CT angiography, V/Q scan, etc.)? (secondary outcome)

3. Background (briefly describe pre-clinical and clinical data, current experience with procedures, drug or device, and any other relevant information to justify the research)

An estimated 180,000 new cases of prostate cancer were diagnosed in 2016, and about 90,000 radical prostatectomies are performed in the United States annually [1-3]. Since the year 2000, a sharp change in practice patterns has shifted the traditionally open radical prostatectomy (RP) procedure to current practice where the great majority (likely >70%) are robotic-assisted laparoscopic RPs (RALRP) [3]. According to most guidelines, undergoing RP by any approach classifies a patient as high-risk for venous thromboembolism (VTE), including deep venous thrombosis (DVT) and pulmonary embolism (PE), and would lead to implementation of appropriate intermittent mechanical pneumatic compression devices (IPCs) and pharmacologic prophylaxis [4-8].

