The primary efficacy outcome will be the incidence of symptomatic VTE within 30 days after surgery. A symptomatic VTE event will be defined as any imaging-confirmed VTE diagnosed after evaluation for VTE prompted by the presence of signs/symptoms concerning for VTE. The primary analysis will compare this rate between treatment arms at the 30-day follow-up for all patients. Symptomatic VTE will also include any deaths attributed to a clinically suspected VTE event without imaging confirmation (if autopsy is performed, VTE must be confirmed at autopsy; if autopsy is not performed, clinical suspicion of VTE as the cause will suffice). Symptoms prompting evaluation include:

1. Persistent unilateral or bilateral lower extremity edema
2. Persistent calf pain or cramping
3. Persistent or new chest pain
4. Persistent or new shortness of breath that started suddenly or worsens with exertion
5. Productive cough with bloody sputum
6. Fever and/or tachycardia without any known source of infection
7. Any other clinical concern for DVT or PE

The primary safety outcomes will include three separate measures of incidence of symptomatic lymphocele, incidence of symptomatic hematoma, or major bleeding within 30 days after surgery. Symptomatic lymphocele and symptomatic hematoma will include imaging confirmed events based on imaging pursued at the discretion of the primary attending urologist per routine practice (current routine practice involves imaging only if clinical symptoms suggest possibility of a lymphocele or hematoma). Events will be recorded regardless of the need for intervention (e.g. drain placement by interventional radiology). While screening studies show rates of 25-50% for postoperative lymphocele regardless of surgical approach (open or robotic), the rate of symptomatic lymphocele is thought to be around 10% or less [31,32]. Major bleeding will be defined as the need for transfusion of ≥ 2 units of packed red blood cells after the completion of surgery for anemia attributed to postoperative bleeding or need to return to the operating room for active bleeding.

c. Secondary outcome variables.

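### Two primary safety outcomes are called symptomatic, but the event definition contains no symptom criterion and leaves imaging to a urologist who knows the arm

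*Combined protocol and SAP*

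**What the plan says.** Section 7b (Primary outcome variable) names the primary safety outcomes as "three separate measures of incidence of symptomatic lymphocele, incidence of symptomatic hematoma, or major bleeding within 30 days after surgery". For two of them the rule reads: "Symptomatic lymphocele and symptomatic hematoma will include imaging confirmed events based on imaging pursued at the discretion of the primary attending urologist". The sentence goes on to tie that imaging to routine practice, and a parenthesis then explains that, at present, scans are done only when the patient's symptoms raise the possibility of a collection. No symptoms are listed, none has to be recorded, and there is no severity threshold: "Events will be recorded regardless of the need for intervention".

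The same section gives the background rates. "While screening studies show rates of 25-50% for postoperative lymphocele regardless of surgical approach", and the symptomatic rate is put at about 10% or less.

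Section 2 (Objectives) words the outcome differently. Aim 2 asks whether heparin will "Increase the incidence of clinically significant lymphocele", and aim 3 uses the same adjective for hematoma.

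On blinding, section 4c states: "Postoperatively, administration of subcutaneous heparin will be unblinded" during the inpatient stay. Control patients get no placebo. Blinded reading is stated only for the leg Duplex screening scan, and no blinded adjudication of lymphocele or hematoma is described. Section 7c records the kind and number of scans after surgery as a secondary outcome, to assess surveillance bias.

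**The concern.** The symptom link for these two outcomes rests on clinicians continuing a habit. If scanning departs from that habit, nothing in the event definition keeps a silent collection out of the count. The plan also does not say how to classify a collection seen on a scan done for another reason.

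This would matter less if the person ordering scans did not know the arm. Here the attending urologist does, and the Abstract (section 1) reports that some urologists already worry about the effect of prophylaxis on lymphoceles and hematomas. If that worry lowers the threshold for scanning heparin patients, the heparin rate rises without any added harm. If scanning runs the other way, a true increase is hidden. At stake is the between-arm comparison that answers aims 2 and 3.

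**Working it through.** **1. The definitions side by side (section 7b).**
- Symptomatic VTE must be confirmed on a work-up set off by signs or symptoms, and seven triggers are listed. The trigger is part of the event.
- Major bleeding has explicit criteria: at least 2 units transfused for postoperative bleeding, or return to the operating room.
- Lymphocele and hematoma need confirmation on discretionary imaging. The symptom trigger appears only as a description of practice.

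**2. The plan's own figure.** The stated N and power (666, or 333 per arm; 82%) belong to VTE, at 5% vs 1.5% and one-sided 0.05. The fixed-sample pooled formula, ignoring the interim looks, gives:
- pooled rate (0.05 + 0.015)/2 = 0.0325
- SE under no difference = √(2 × 0.0325 × 0.9675/333) = 0.01374
- SE under the alternative = √((0.0475 + 0.014775)/333) = 0.01368
- power = Φ((0.035 − 1.645 × 0.01374)/0.01368) = 81.8%

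This agrees with the stated 82%. A change to the lymphocele and hematoma definitions does not alter N. The plan gives no power figure for the safety outcomes.

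**3. Silent lymphocele share.** Screening rate minus symptomatic rate: 25% − 10% = 15%, and 50% − 10% = 40%. A symptomatic rate below 10% would make this share larger.

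**4. Illustration for lymphocele.** Let f be the share of patients in one arm who are imaged without symptoms, over and above the other arm. The documents do not give f, so it is an assumption. So is the two-sided 0.05 test, because sidedness for safety is not stated. With no true heparin effect and 10% in controls:

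observed heparin rate = 10% + f × (15% to 40%)

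P(false significant excess) = Φ((d − 1.96 × SE₀)/SE₁), where d is the rate difference, SE₀ the pooled standard error and SE₁ the unpooled one, with 333 per arm.

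| f | Heparin-arm rate | Extra events per 333 | P(false excess) |
|---|---|---|---|
| 0 | 10.0% | 0 | 2.5% |
| 5% | 10.8-12.0% | 2.5-6.7 | 5-13% |
| 10% | 11.5-14.0% | 5.0-13.3 | 9-35% |
| 20% | 13.0-18.0% | 10.0-26.6 | 23-85% |

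The f = 10% row in full:
- low end: d = 0.015, SE₀ = SE₁ = 0.02400, argument −1.335, probability 0.091
- high end: d = 0.040, SE₀ = 0.02518, SE₁ = 0.02514, argument −0.372, probability 0.3548

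**5. Interim lymphocele limit (section 7e).** A halt for review needs the lower 95% bound to reach 15%. With exact two-sided limits the smallest qualifying counts are 25/111 (22.5%), 45/222 (20.3%) and 83/444 (18.7%). These sizes cover one arm or both arms at the two looks, since the plan does not say which is meant. From a 10% base, the observed rate must rise by about 9 to 12 points. The 1.5-4.0 points from step 4 at f = 10% fall well short.

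**6. Hematoma.** No screening rate is given, so no such calculation is possible.

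**The case against.** The strongest reply is that the plan does tie these events to symptoms. The outcome is named symptomatic, the imaging is to follow routine practice, and that practice is described as symptom-driven. A reader who stops before those words might infer that any collection counts with no symptom link at all. The documents do not support that. What stands is narrower: the link describes practice and is not a condition for counting an event.

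The contrast with VTE is also one of degree, since both definitions work through what triggers imaging and the VTE list ends with an open item for any other clinical concern. Even so, the VTE trigger is written into the event and the other is not.

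Three further inferences go too far.
- A reader might take the plan to count incidental findings on scans done for other reasons. It is silent on them, which is an ambiguity and not a rule.
- A reader might argue that fewer VTE work-ups on heparin would hide lymphoceles. The studies named in section 2 are of the leg or chest, and nothing in the documents suggests they would show a pelvic collection.
- A reader might equate clinically significant with needing intervention. The documents do not define it so, and counting symptomatic events that need no drainage is defensible.

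Finally, the plan compares imaging use between arms as a secondary outcome. That can reveal unequal scanning, which is a real safeguard, but it does not correct the event counts. The indication for each scan is not among the items to be recorded.

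**Conclusion.** The point holds as a gap in the definition of two primary safety outcomes, made more important by open treatment after surgery and the absence of described blinded adjudication. It is worth correcting and does not undermine the trial as a whole.

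For lymphocele, each 10 percentage points of extra non-symptom imaging of the area in one arm would add about 1.5-4.0 points to that arm's rate. In the illustration this gives about a 9-35% chance of a false significant excess, against 2.5%. The result rests on the assumed imaging difference, a 10% symptomatic rate in both arms, 333 per arm and a two-sided 0.05 test. If nobody is imaged without symptoms, there is no bias. The documents fix neither its actual size nor its direction, and they support no figure for hematoma.

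Two larger readings are not supported. The full 25-50% cannot be treated as silent, because it is the total screening rate. Nor can the 5 points between a 10% expected rate and the 15% limit be treated as the margin before a halt, because the rule uses the lower confidence bound. The main exposure is the final safety comparison.

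**What to change.** In section 7b, count a lymphocele or hematoma as a primary safety event only if the imaging that showed it was prompted by a recorded sign or symptom suggesting a collection, in parallel with the VTE definition. In addition:
- Record the indication for each postoperative scan alongside the imaging data already collected under section 7c.
- List collections found on imaging done for other reasons separately, and report the between-arm comparison with and without them.
- Use one term, either symptomatic or clinically significant, in sections 2 and 7b.

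Classification of events by someone unaware of the arm would be a useful addition where feasible.

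The core change costs a definition sentence and one or two extra chart-review fields. Slightly fewer events will be counted. The sample size is unaffected, since it rests on VTE.

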Patients randomized to the pharmacologic VTE prophylaxis arm will receive a dose of subcutaneous heparin 5,000 units within 2 hours prior to incision, and subcutaneous heparin 5,000 units every 8 hours after surgery until discharge. Total number of doses received and missed doses will be recorded. No post-discharge pharmacologic prophylaxis will be prescribed. Per routine care, patients will be requested to inform their urologist's office if they experience any symptoms of DVT or PE, or any other concerns, during the first 30 days after surgery. All patients will receive a phone call around 30 days after surgery to assess primary outcomes including documentation of whether they experienced a postoperative VTE episode and any treatment initiated for confirmed VTE. Any patient endorsing symptoms concerning for VTE up to 30 days after surgery will be recommended to undergo urgent evaluation and care, locally or at Johns Hopkins, with imaging/evaluation results forwarded to Johns Hopkins. Patients and their insurance will be responsible for the costs as part of routine care. The 30-day phone call will be the only planned, study-initiated contact after surgery with the patient to evaluate symptomatic outcomes and will be the same for both the control and pharmacologic prophylaxis arms.

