The secondary outcomes (all regarded separately) will be estimated blood loss from surgery, total surgical drain output after surgery (for patients with surgical drains), the overall incidence of VTE (asymptomatic or symptomatic) determined from the subcohort undergoing lower extremity Duplex screening ultrasound, and surveillance bias (measured by use of postoperative diagnostic imaging). Estimated blood loss will be recorded from the anesthesia data report from surgery. Total surgical drain output will be recorded based on ins and outs flowsheets routinely recorded by nurses when emptying drains. Surveillance bias will be determined by recording the type and frequency of postoperative imaging performed while a patient is in the hospital or within 30 days of surgery after discharge.

The overall rate of VTE will only be determined for patients in the subcohort. The asymptomatic VTE will be determined based on the results of the screening lower extremity Duplex ultrasound for asymptomatic DVTs. The overall rate of VTE will be determined by adding the number of asymptomatic VTE events to the number of symptomatic VTE events experienced in the subcohort.

d. Statistical plan including sample size justification and interim data analyses.

Pharmacologic VTE prophylaxis can be expected to prevent between 67% to 75% of DVTs [33]. Given the lowest expected primary outcome event rate will be for VTE, the trial sample size will be based on a power of 80% ($\beta=0.2$) and one-sided α of 0.05 for prevention of post-operative VTE with pharmacologic prophylaxis reducing the rate from 5% to 1.5%. Including two interim analyses of the primary endpoint as outlined in the Interim Analyses section below, the total sample size needed will be 666 (333 per treatment arm) based on 2000 simulations for 82% power (exact α -spending and futility boundaries are outlined below). As mentioned above, the primary efficacy analysis will compare symptomatic VTE rates at the 30-day follow-up for all patients. Secondary analyses will be conducted to compare secondary outcomes between treatment arms at the completion of the study as well. It is expected that during full-time patient enrollment, the study would require about 2 years to accrue patients assuming 50% enrollment.

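### The plan blinds urologists to protect recorded blood loss but takes the value from the anesthesia report without saying who makes the estimate, so blinding of that value is not assured

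*Combined protocol and SAP*

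**What the plan says.** Blood loss during surgery is aim 6 in section 2 (Objectives) and is classed there as a secondary outcome.

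Section 4c (Blinding) states the protective measure and its purpose together: "Urologists will initially be blinded to patient randomization and the administration of the preoperative subcutaneous heparin dose to prevent bias on recorded estimated blood loss". Heparin is given unblinded after surgery. The same section says "Control patients will receive IPCs only and no placebo doses will be administered during their hospital stay". It names two other blinded activities: "Data analysis will be blinded as to treatment group" and "Performance and interpretation of lower extremity Duplex screening ultrasound will be blinded to patient randomization".

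Section 7c (Secondary outcome variables) names the data source: "Estimated blood loss will be recorded from the anesthesia data report from surgery".

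On the dose, section 4a (Study design) says that patients in the heparin arm "will receive a dose of subcutaneous heparin 5,000 units within 2 hours prior to incision". Section 7a (Randomization scheme) has the assignment passed to the study coordinator. No section says who then gives the preoperative dose or who can see that it was given.

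**The concern.** The people blinded for the sake of this outcome are urologists, yet the outcome is read from the anesthesia team's document. If someone who knows the allocation makes the estimate, expectation can enter it. Because the plan gives bias in recorded blood loss as its reason for blinding, it already treats the measure as open to such influence.

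If estimates in the heparin arm drifted upward for that reason, the comparison could suggest that heparin increases operative bleeding when it does not. Urologists' worry about bleeding is part of the reason for the trial, so readers will look at this result. It would be presented as coming from a blinded assessment, and the protocol as written does not let them confirm that it was.

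**Working it through.** **Step 1: set the provisions side by side.**

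| Question | What the protocol says | Where |
|---|---|---|
| Who is blinded to the preoperative dose? | Urologists are the only operating-room staff named | 4c |
| Why? | To keep bias out of recorded blood loss | 4c |
| Where does the value come from? | The anesthesia report | 7c |
| Who makes the estimate in that report? | Not stated | – |
| Are anesthesia staff blinded? | Not stated | – |
| Is the preoperative dose masked by a placebo? | None described; none given during the hospital stay | 4c |
| Who gives the dose, and who can see it? | Not stated | – |

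The other two blinded activities, data analysis and the Duplex scan, come after the blood-loss figure has been written down and cannot affect how it was formed.

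**Step 2: the two possible readings.**

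- The anesthesia report carries the urologist's own estimate. Sections 4c and 7c then fit together and the value is protected.
- Anesthesia or other staff make the estimate. Nothing in the plan keeps them from knowing the allocation, so the value is not assured to be blinded.

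The text is compatible with both.

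**Step 3: the plan's own figures.** The protocol gives no SD, target difference or power for blood loss, so there is no figure to reproduce for this outcome. The 333 per arm used below is the plan's sample size for symptomatic VTE (sections 7d and 7e). It reproduces: for 5% versus 1.5%, one-sided alpha 0.05 and 333 per arm, a pooled two-proportion test without continuity correction has power 0.818, against 82% stated. The present point leaves it unchanged.

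**Step 4: illustration of sensitivity.** All inputs except 333 per arm are assumptions: SD of 200 or 500 mL, a pure recording shift δ of 15, 30 or 60 mL, no true effect, and a two-sided 5% test with a normal approximation.

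SE = SD × √(2/333) = SD × 0.0775. This is 15.5 mL at SD 200 and 38.7 mL at SD 500.

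Rejection probability = Φ(δ/SE − 1.96) + Φ(−δ/SE − 1.96).

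| Shift δ | δ/SE, SD 500 | Rejection, SD 500 | δ/SE, SD 200 | Rejection, SD 200 |
|---|---|---|---|---|
| 15 mL | 0.39 | 7% | 0.97 | 16% |
| 30 mL | 0.77 | 12% | 1.94 | 49% |
| 60 mL | 1.55 | 34% | 3.87 | 97% |

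The table shows that a test of this size would respond to modest recording shifts. It is not evidence that such a shift will occur here.

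**The case against.** The strongest reply is that section 7c names the document from which the value is extracted, not the person who judged it. The rationale in section 4c makes most sense if the authors took the urologist to supply or influence the recorded figure; on that reading the plan is coherent. This stands as a plausible reading. It is not stated anywhere, so it does not close the gap.

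Three further points stand:

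- Blinding the surgeon does useful work in any case. It keeps knowledge of allocation from altering operative behaviour, and hence true blood loss, and from colouring anything the surgeon tells the person recording it.
- The illustrative rejection rates depend entirely on assumed SDs and shifts, as does the upward direction. They carry no weight as a forecast.
- Bleeding safety rests on other outcomes: major bleeding defined by transfusion or return to the operating room, and imaging-confirmed hematoma (section 7b). Those, with lymphocele, are what the safety review in section 7e examines. Blood loss drives no sample size, interim look or stopping rule.

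A reader might also infer that the problem reaches the primary endpoints, because section 7d lists blood loss among the factors checked for imbalance and allows adjusted logistic regression. The documents do not support that as a finding. The named primary analysis is an unadjusted chi-squared test, adjustment is conditional on an imbalance, and nothing shows that a recording difference will arise.

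**Conclusion.** The concern holds in a limited form. The protocol states a purpose for its intraoperative blinding, to protect recorded blood loss, and does not secure that purpose for the data source it names. Blinding of the value is not assured, and it is protected only if the anesthesia report carries the blinded urologist's figure.

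A reader might go further and conclude that the blinding fails, or that anesthesia staff know who received heparin. The documents support neither. They are silent on who makes the estimate, who gives the dose and who sees it.

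The effect is confined to one secondary outcome. Its size is unknown, since the protocol gives no SD for blood loss and no basis for a recording shift; the range of 7% to 97% across the assumed scenarios is illustrative only. The point still merits a change because the gap is cheap to close beforehand and cannot be repaired once the estimates have been recorded.

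**What to change.** In section 7c, define estimated blood loss as the operating urologist's own estimate, entered in a study data field at the end of surgery while that urologist is still blinded. Add to section 4c that this entry must precede unblinding. Keep the anesthesia report value and analyse it in the same way as a sensitivity analysis.

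The same edit should state who makes and enters the anesthesia figure and whether that person knows the allocation, so that any disagreement between the two values can be interpreted.

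The cost is a line in each of the two sections, one extra data field, and two values to reconcile for each patient. If the anesthesia report already carries the urologist's figure, the new field will largely duplicate it, and little is lost. Extending blinding to whoever enters the anesthesia estimate is an alternative, but without a placebo it would need procedural arrangements that the plan does not now contain. Treatment, sample size and the primary endpoints stay as they are.
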